2.15.5.3 Long-Term Safety

2.15.5.3.1 Long-term Safety – Control

The one-year rate for the control safety endpoint of major bleeds and all-cause mortality was derived from the same literature review as cited

above (Connolly 2009, Granger 2011, Patel 2011) for effectiveness endpoint determination.

In sum:

Safety event rates from the OAC literature listed the following one-year event rates:

- RE-LY treatment arm (N=6076, dabigatran) = 6.75%
- RE-LY control arm (N=6022, warfarin) = 7.49%
- ARISTOTLE control arm (N=9081, warfarin) = 7.03%
- ROCKET AF control arm (N=7133, warfarin) = 8.37%

The weighted average of these three trials is 7.17% (assuming a 50% adoption rate of dabigatran) endpoint events per year.

The distribution of dabigatran and warfarin use will be monitored during the course of the trial. If a significant deviation from the expected adoption rate is observed, its potential impact will be assessed and appropriate adjustments to base rates and sample size calculations may be re-visited and/or re-modeled as appropriate.

2.15.5.3.2 Long-term Safety – Device

The one-year rate for the device safety pivotal endpoint of major bleeds and all-cause mortality was also derived from published experience to-date with the ACP device.

- Safety endpoints from the feasibility phase were:
1/30 (3.3%) (six months)
- Safety endpoints from the ACP Registry (ACPR) were:
10/197 (5.1%) (six months)

The weighted average of these two trials is 4.85% endpoint events per six months. To estimate a one-year rate from these six-month endpoints, Kaplan-Meier curves were analyzed from the PROTECT AF study (SSED). This analysis showed an increase of 6.2% from six months to one year for the primary safety endpoint. Employing this percent change over time corresponds to a one-year rate of 5.15%, the primary rate used for the calculations of the device safety endpoint.

2.15.5.3.3 Operating Characteristics, Power, and Type I Error

For the Bayesian adaptive design the power will be calculated using simulations. Besides design features described above, three other factors contribute to the study's power: the true unknown event rate, the unknown accrual rate, and the lost-to-follow-up rate observed in study subjects. The accrual rate can be controlled to some extent by the number of sites and

inclusion criteria, and the event rate can be projected based on the study's inclusion criteria.

To find operating characteristics, 1000 trials are simulated from each of 10 different scenarios. To simulate trials the following assumptions are made about the data-generating process. These are necessary to estimate operating characteristics but will not be used in the analysis of the actual trial.

- Times to efficacy events have an exponential distribution within each time period in both the device and control arms with the specified rate
- Times to safety events have an exponential distribution in both the device and control arms with the specified event rate
- There is 5% yearly lost-to-follow-up.
- Accrual is constant 25 subjects per month. (While accrual is not expected to be constant during the ACP trial, it is expected to be lower earlier and then stabilize after all sites have begun enrollment. If this is the case, then early subjects will have greater follow-up and the power calculations below will be underestimates.)

Operating characteristics have been calculated for a variety of accrual rates, efficacy event rates and safety event rates.

Tables 4a and **4b** illustrate the 10 scenarios used. Each row shows one parameter used to generate trial data used in the simulations.

Scenarios 1-4 in **Table 4a** represent Scenarios in the null space where Type I error should be 2.5% or less. Scenario 1 is when the device is neither non-inferior for efficacy nor superior for safety. Scenario 2 fails to meet the definition for efficacy non-inferiority, Scenario 3 fails to meet the definition for superiority for safety. The efficacy scenarios are shown where Type I error should be the highest. Scenario 4 shows the Type I error rate for the expected control event rate for efficacy. The six scenarios in **Table 4b** illustrate cases where the ACP device is non-inferior for efficacy and superior for safety.

Table 4a. Scenarios for 4 NULL cases where non-inferior efficacy and/or superiority safety case is not met.

Scenario	1	2	3	4
$\lambda_{C,1}$	0.019497	0.019497	0.014972	0.019497
$\lambda_{C,2}$	0.019497	0.019497	0.014972	0.019497
$\lambda_{C,3}$	0.019497	0.019497	0.014972	0.019497
$\lambda_{C,4}$	0.019497	0.019497	0.014972	0.019497
$\lambda_{C,5}$	0.019497	0.019497	0.014972	0.019497
$\lambda_{C,6}$	0.019497	0.019497	0.014972	0.019497
$\lambda_{C,7}$	0.019497	0.019497	0.014972	0.019497
$\lambda_{D,0}$	0.034635	0.034635	0.014972	0.034635
$\lambda_{D,1}$	0.034635	0.77	0.77	0.77
$\lambda_{D,2}$	0.034635	0.0274	0.00756	0.0274
$\lambda_{D,3}$	0.034635	0.0274	0.00756	0.0274
$\lambda_{D,4}$	0.034635	0.0274	0.00756	0.0274
$\lambda_{D,5}$	0.034635	0.0274	0.00756	0.0274
$\lambda_{D,6}$	0.034635	0.0274	0.00756	0.0274
$\lambda_{D,7}$	0.034635	0.0274	0.00756	0.0274
π_C	3.82%	3.82%	2.95%	3.82%
π_D	6.69%	6.69%	2.95%	6.69%
$\pi_D - \pi_C$	2.87%	2.87%	0.00%	2.87%
π_D / π_C	1.75	1.75	1.0000	1.75
γ_C	0.0717	0.0717	0.0717	0.0717
γ_D	0.0717	0.0717	0.0717	0.0515
γ_D / γ_C	1	1	1	0.718
Efficacy	NULL	NULL	Non-inf	NULL
Safety	NULL	NULL	NULL	Superior

Table 4b. Scenarios for 6 cases where non-inferior efficacy and superiority safety case are met.

Scenario	5	6	7	8	9	10
$\lambda_{C,1}$	0.01497	0.01497	0.01497	0.01497	0.00749	0.02246
$\lambda_{C,2}$	0.01497	0.01497	0.01497	0.01497	0.00749	0.02246
$\lambda_{C,3}$	0.01497	0.01497	0.01497	0.01497	0.00749	0.02246
$\lambda_{C,4}$	0.01497	0.01497	0.01497	0.01497	0.00749	0.02246
$\lambda_{C,5}$	0.01497	0.01497	0.01497	0.01497	0.00749	0.02246
$\lambda_{C,6}$	0.01497	0.01497	0.01497	0.01497	0.00749	0.02246
$\lambda_{C,7}$	0.01497	0.01497	0.01497	0.01497	0.00749	0.02246
$\lambda_{D,0}$	0.01497	0.01497	0.01497	0.01497	0.00749	0.02246
$\lambda_{D,1}$	0.77	0.01497	0.4	0.114	0.385	1.155
$\lambda_{D,2}$	0.00756	0.01497	0.068	0.114	0.00378	0.01134
$\lambda_{D,3}$	0.00756	0.01497	0.068	0.114	0.00378	0.01134
$\lambda_{D,4}$	0.00756	0.01497	0.00756	0.00756	0.00378	0.01134
$\lambda_{D,5}$	0.00756	0.01497	0.00756	0.00756	0.00378	0.01134
$\lambda_{D,6}$	0.00756	0.01497	0.00756	0.00756	0.00378	0.01134
$\lambda_{D,7}$	0.00756	0.01497	0.00756	0.00756	0.00378	0.01134
π_C	2.95%	2.95%	2.95%	2.95%	1.49%	4.39%
π_D	2.95%	2.95%	2.95%	2.95%	1.49%	4.39%
$\pi_D - \pi_C$	0.00%	0.00%	0.00%	0.00%	0.00%	0.00%
π_D / π_C	1.00	1.00	1.00	1.00	1.00	1.00
γ_C	0.0717	0.0717	0.0717	0.0717	0.0717	0.0717
γ_D	0.0515	0.0515	0.0515	0.0515	0.0515	0.0515
γ_D / γ_C	0.7183	0.7183	0.7183	0.7183	0.7183	0.7183
Efficacy	Non-inf	Non-inf	Non-inf	Non-inf	Non-inf	Non-inf
Safety	Superior	Superior	Superior	Superior	Superior	Superior

Table 5 summarized the operating characteristics for each scenario. Each two rows show one scenario. The columns reflect the summary statistics for the 1000 simulations per scenario:

Mean N	Mean sample size
SD N	Standard deviation of sample size
Stop Early	Proportion of trials that stop early for predicted success
Stop Max	Proportion of trials that accrue to maximum 3000 subjects
Stop Futility	Proportion of trials that stop early for futility
Efficacy Power	Proportion of trials that meet either definition of non-inferiority efficacy success
Ratio	Proportion of trials with $\Pr(\pi_D/\pi_c < 1.75) \geq 0.988$
Diff	Proportion of trials with $\Pr(\pi_D - \pi_c < 2.87\%) \geq 0.988$
Safety Power	Proportion of trials that meet safety definition of superiority success, $\Pr(\gamma_D / \gamma_C < 1.0) \geq 0.992$.
Power	Proportion of trials meeting both efficacy and safety goals.
N 0-1	Mean number of patients with less than 1 year of follow-up in successful trials (trials meeting efficacy and safety endpoints)
N 1-2	Mean number of patients with 1-2 years of follow-up in successful trials (trials meeting efficacy and safety endpoints)
N 2+	Mean number of patients with greater than 2 years of follow-up in successful trials (trials meeting efficacy and safety endpoints)

The second line in each scenario shows the same success probabilities if the analysis is repeated using an as-treated analysis that censors subjects randomized to the device who crossover and use warfarin 45 days or more after their procedure. Simulations verify that adequate power is maintained to interpret the primary effectiveness endpoint. For a detailed calculation please refer to the second line (AT = As Treated) under each scenario in **Table 5**. Here we assume 9% of subjects crossover immediately, 12.5% are censored at 45-days, then 5% are censored per year.

Scenarios 1-4 and show that Type I errors rate are all $\leq 2.5\%$ (in bold). In these situations trials stop early for futility 88 – 100% of the time. The same “Power” column shows powers for the safe and efficacious scenarios. For example Scenario 5, the expected scenario, has 91% power. For other safe (superior) and efficacious (non-inferior) scenarios the trial offers $\geq 89\%$ power.

In this expected scenario (5) the average sample size is 1880 subjects and the trial stops early for predicted success 88% of the time. The average trial size in the null cases is 906-1919.

While the trial’s sample size may range from 400 to 3000 subjects, the average trial size, which varies by scenario, ranges from 906 to 2350 subjects for the scenarios shown here.

Scenarios 5-9 illustrate safe and efficacious cases. In these scenarios, the average number of patients with two or more years of follow-up ranges from 1303-1816 patients.

Table 5- Operating Characteristics for Bayesian Adaptive Design

Scenario	Mean N	SD N	Stop Early	Stop Max	Stop Futility	Efficacy Power	Ratio	Diff	Safety Win	Power	N 0-1	N 1-2	N 2+	Analysis
1	906	396	0.000	0.000	1.000	0.000	0.000	0.000	0.000	0.000	--	---	---	ITT
						0.000	0.000	0.000	0.000	0.000	--	---	---	AT
2	1046	524	0.001	0.002	0.997	0.002	0.001	0.002	0.001	0.001	205	316	579	ITT
						0.001	0.001	0.001	0.001	0.001	417	276	407	AT
3	1549	765	0.016	0.057	0.93	0.072	0.043	0.072	0.018	0.018	241	344	1751	ITT
						0.018	0.008	0.018	0.004	0.004	640	305	843	AT
4	1919	832	0.010	0.11	0.88	0.022	0.016	0.017	0.117	0.022	245	369	2100	ITT
						0.010	0.009	0.010	0.020	0.010	806	347	1346	AT
5	1880	645	0.88	0.060	0.059	0.93	0.38	0.93	0.93	0.91	232	356	1356	ITT
						0.84	0.28	0.84	0.61	0.55	670	320	996	AT
6	2350	712	0.57	0.32	0.11	0.89	0.55	0.89	0.89	0.88	260	380	1816	ITT
						0.87	0.39	0.87	0.68	0.67	814	354	1316	AT
7	1941	672	0.84	0.094	0.069	0.93	0.41	0.93	0.92	0.92	234	355	1431	ITT
						0.85	0.32	0.85	0.63	0.58	683	321	1023	AT
8	1991	707	0.79	0.12	0.091	0.90	0.43	0.90	0.90	0.90	241	362	1493	ITT
						0.85	0.34	0.85	0.64	0.60	705	28	1069	AT
9	1819	648	0.88	0.050	0.070	0.93	0.20	0.93	0.92	0.92	229	351	1303	ITT
						0.90	0.16	0.90	0.59	0.58	636	311	917	AT
10	2163	726	0.68	0.23	0.087	0.88	0.69	0.88	0.90	0.87	247	369	1629	ITT
						0.76	0.55	0.76	0.64	0.55	757	342	1180	AT

Scenario 5 is illustrated below. The first section shows the number of simulations and design characteristics as described above.

```

Simulations           =      1000
Minimum Sample Size  =      400
Frequency of looks (pts) =      50
Maximum Sample Size  =     3000
Accrual Rate         =     25.0
Posterior Prob Win Eff =    0.9880
Posterior Prob Win Saf =    0.9920
Ratio < to Win       =    1.7500
Diff < to Win        =    0.0287
  
```

The second section shows the parameters used to simulate the efficacy events. The bottom lines within the “True Efficacy Event Rate” subsection show the 2-year event rate (2.15% vs. 3.15% here) and the ratio & difference. The “True Safety Event Rate” subsection shows the event rate assumed through follow-up for the warfarin group and after day discharge for the device group. This also shows the risk ratio and risk difference.

```

True Efficacy Event Rate
  Month   Control   Month   Treatment
  True Efficacy Event Rate
          0-proc   0.0150
0 - 6    0.0150   pr -p+6  0.7700
6 - 30   0.0150   p+7- 30  0.0076
31 - 60  0.0150   31 - 60  0.0076
60 - 6m  0.0150   60 - 6m  0.0076
6 - 12   0.0150   6m - 12  0.0076
12 - 18  0.0150   12 - 18  0.0076
18 - 24  0.0150   18 - 24  0.0076
2-year   0.0295   2-year   0.0295
Ratio =   1.0000   Diff =   0.0000

True Safety Event Rate
Annual   0.0717   Annual   0.0515
Ratio =   0.7183   Diff =  -0.0202
  
```

The final section shows the operating characteristics.

```

MaxN  Acc  MeanN  SD N  Mnth  SGood  StEnd  StFut  EffWn  Ratio  Diff  SFwin  E&SWin
3000  25.0  1880.  645.  81.7  0.881  0.060  0.059  0.925  0.384  0.925  0.928  0.914

      CEEv  TEEv  CEEvp  TEEvp  CSEv  CSEv  CSEvp  TSEvp  0-1  1-2  2+
      32.  51.  2145.  4302.  135.  202.  1882.  3925.  232.  356.  1356.

      AS TREATED  AnyWn  Ratio  Diff  SFwin  E&SWin
      0.840  0.283  0.840  0.605  0.552
  
```

These show the maximum sample size (MaxN) and accrual rate (Acc) plus the mean (MeanN) and standard deviation (SD N) of the sample size and the proportions of simulated trials that stop early for predicted success (SGood), run to the maximum sample size (StEnd), and stop for futility (StFut). In this scenario 88.1% stopped for predicted success, 5.9% ran to 3000 subjects and 5.9% stopped early for futility.

The next five values show the statistical power. The probability of demonstrating efficacy non-inferiority is shown (EffWn) and further broken down by the proportion that achieve the risk ratio < 1.75 (Ratio) or risk difference < 2.87% (Diff). The probability of demonstrating superiority for safety

(SFwin) and both non-inferiority for efficacy and superiority for safety (E&SWin) are also shown. Here there is a 92.5% chance of achieving the efficacy goal, predominantly via the risk difference, a 92.8% chance of achieving the safety goal, and a 91.4% chance of achieving both.

The second line summarizes the events and exposure. CEEv, DEEv, CEEp, and DEEp show the mean number of efficacy events in the control group, efficacy events in the device group, years of exposure for efficacy in the control group, and years of exposure for efficacy in the device group. CSEv, DSEv, CSEp, and DSEp are the same for safety events.

The final three values 0-1, 1-2, and 2+ show the mean number of subjects with 0 to 1, 1 to 2, or 2 more years of exposure for successful trials. These last three figures summarize only trials in which the efficacy and safety goal are met, the idea being to relay the expected amount of follow-up times if success is declared.

The final line shows the win rates in the as treated analysis. These analyses are performed only if both the efficacy and safety goals are met in the intent-to-treat analysis.

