2.15.3 Study Design (REFER TO APPENDIX D)

The study is intended to determine the difference in efficacy and safety between the device arm and control arm (subjects treated with OMT).

The ACP clinical trial is an adaptive design with interim sample size analyses that use current data and project the necessary sample size and follow-up time based upon observed efficacy and safety event rates in the device and control subjects.

Three primary endpoints and hypotheses are being evaluated in the ACP clinical trial

1. An efficacy endpoint which compares the 2-year event rates of ischemic stroke and peripheral thromboembolism. This is a non-inferiority analysis where the device will be deemed efficacious if the risk ratio is < 1.75 or the risk difference in two years event rates is < 2.87 .
2. A long-term safety endpoint which compares long-term composite rates of all-cause mortality and major bleed. This is a superiority analysis where the device will be deemed safe if the safety event rate in the device arm is proven superior to the safety event rate in the control arm (OMT).
3. An acute safety (short-term) endpoint which compares the rate of device or procedure related serious adverse events against a performance goal (PG). If this

rate is less than 5%, the device is considered to have met the acute safety endpoint.

The primary efficacy and primary long-term safety hypotheses are included in the adaptive design. The study will accrue subjects until there is high predictive probability that the sample size is sufficient to meet the efficacy and long term safety endpoints or until it is evident that in spite of enrolling to the maximum sample size it is unlikely to meet the efficacy and long-term safety endpoints.

The analysis for the primary acute safety endpoint will be performed on the entire sample size as determined by the adaptive design governed by the efficacy and long term safety endpoints.

The ACP clinical trial is powered to concurrently prove the non-inferiority efficacy endpoint, along with the acute and long-term safety endpoints. The precise follow-up time may vary in this adaptive design.

Interim sample size analyses will be performed when 400 subjects are enrolled, then again every 50 subjects until a possible maximum of 3000 subjects are obtained. Once subject accrual is stopped and the predictive probability of trial success for both efficacy and long-term safety is high, all subjects will be followed for at least 6 months.

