2.15.3.4 Primary Safety Endpoints and Hypotheses

The **primary safety endpoint** for the ACP study has two components: acute safety and long-term safety.

- a. Acute safety consists of procedure related serious adverse events that qualify as one of the following:
 - procedure-related death (i.e., death occurring during the implantation procedure).
 - pericardial effusion requiring treatment.
 - device embolization.
 - access site-related bleeding requiring transfusion ≥ 2 units.
 - damage to other cardiac or major non-cardiac cardiovascular structures

The acute analysis does not inform the adaptive design in that its probability of success does not affect the adaptive sample size algorithm.

In the acute safety analysis, the rate of device or procedure related serious adverse events from the time of randomization until hospital discharge is compared against a performance goal (PG) of 5.0% chosen from the literature.

Let π_{DEVICE} be this pre-discharge event rate in the device arm. Specifically, the following null and alternative hypotheses will be tested:

$$H_0: \pi_{\text{DEVICE}} \geq (\text{PG} = 5.0\%)$$

$$H_a: \pi_{\text{DEVICE}} < (\text{PG} = 5.0\%)$$

The null hypothesis will be rejected and the performance goal will be considered met if the upper bound of the one-sided confidence interval for the device rate is less than 5.0%.

- b. Long-term safety events can occur in either the device arm or the control arm and consist of the following:
 1. All-cause death; or
 2. Major bleeding defined as:
 - a. Symptomatic intracerebral or intraventricular hemorrhage; or subdural, subarachnoid, epidural, or ocular hemorrhage; or
 - b. Major non-cerebral bleed-defined as transfusion requiring ≥ 2 units, hospitalization requiring any transfusion or surgical or percutaneous interventional procedure to treat bleeding

Note: procedure-related pericardial effusions requiring treatment will not be counted as a major non-cerebral bleed

Subjects who experience a non-fatal efficacy event are still followed and included in the safety analysis.

The long-term safety analysis is a two-arm analysis that compares the safety events defined above between the device and the control arm. For both the device arm and the control arm, the events will be evaluated from the time of randomization until two years. This analysis will test for superiority of the device arm versus the control arm.

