2.15.5.2 Primary Safety

2.15.5.2.1 Procedural (Acute) Safety- This analysis compares the rate of procedure related serious adverse events (SAE) as listed below, that occur in the device arm from the time of randomization until hospital discharge to a performance goal (PG) chosen from the literature. The endpoint will be considered met if the 96% credible interval for the in-hospital event rate is entirely less than the PG.

- procedure-related death (i.e., death occurring during the implantation procedure).
- pericardial effusion requiring treatment.
- device embolization.
- access site-related bleeding requiring transfusion ≥ 2 units.
- damage to other cardiac or major non-cardiac cardiovascular structures

A literature search was conducted in order to establish a PG. The search criteria included catheter ablation for atrial fibrillation. This criterion was chosen because catheter ablation utilizes transseptal puncture to access the left atrium which is the common technique used to access the left atrial appendage and implant the ACP device. The search included electrophysiologic (EP) studies and summaries of safety and effectiveness (SSED).

In all, 29 sources (27 published articles and two SSEDs) were examined for reported complications of procedure related SAE (as listed above). Serious Adverse Events of procedure-related death (i.e., death occurring

during the implantation procedure), access site-related bleeding requiring transfusion ≥ 2 units and device embolization was clearly reported. The Atritech SSED served to provide an estimate of the rate for device embolization since the EP literature would lack this complication. However, in order to categorize literature reported complication against 'pericardial effusion requiring treatment' and 'Damage to other cardiac or major non-cardiac cardiovascular structures' the following criteria were used:

- Pericardial effusion requiring treatment included pericardial effusions that required pericardiocentesis and cardiac tamponade. Also included within this category are pericardial effusions that were medically treated, or where treatment was not specified. Please note this category does not include effusions that were spontaneously resolved.

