- Damage to other cardiac or major non-cardiac cardiovascular structures included serious complications requiring more than conservative medical attention such as pleural effusion, pneumo- or hemothorax, lung injury, pulmonary edema, valve damage, vascular injury including arteriovenous fistulae requiring surgical intervention, aortic dissection, aortic root puncture and coronary sinus perforation.

The average weighted complication rate derived from literature Meta-analysis is provided in **Table 3**.

Table 3- Performance Goal

Death (procedure-related)	Device Embolization	Access Site Bleeding (requiring ≥ 2 units)	Damage to Other Cardiac or Major Non-Cardiac Cardiovascular Structures	Pericardial Effusion (requiring treatment)
0.05%	0.22 %	2.97%	0.46%	1.23%
Average Weighted Complication Rate= 4.93%				

Therefore a performance goal of 5% is being established, against which the acute safety profile of the ACP device will be compared. A performance goal of 5% provides confidence that it adequately represents a threshold between event rates observed in literature and is clinically relevant. The ACP trial will meet its acute safety success if the two-sided 95% credible interval lies entirely below this PG.

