1.5 DURATION OF THE INVESTIGATION AND SAMPLE SIZE

A total of 97 subjects were enrolled in the trial at 17 centers. Safety data collected will be summarized in a final report. No additional subjects or centers will be added to the study.

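### Should the plan's claim of at least 89% power, and of power for acute safety, be corrected when Table 5 shows 0.88 and 0.87 and covers two endpoints only?

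*Combined protocol and SAP*

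**What the plan says.** Section 2.15.5.3.3 directs the reader to the Power column of Table 5. It cites 91% for Scenario 5 and then states: "For other safe (superior) and efficacious (non-inferior) scenarios the trial offers" at least 89% power. The same section defines that column as "Proportion of trials meeting both efficacy and safety goals", where safety means long-term superiority at a posterior probability of 0.992. Table 4b lists six success scenarios (5 to 10), while the text introducing Table 5 says "Scenarios 5-9 illustrate safe and efficacious cases".

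Section 2.15.3 makes a wider claim: "The ACP clinical trial is powered to concurrently prove the non-inferiority efficacy endpoint, along with the acute and long-term safety endpoints".

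The acute success rule appears in three places:
- Section 2.15.3.4: "the performance goal will be considered met if the upper bound of the one-sided confidence interval for the device rate is less than 5.0" per cent, with no confidence level.
- Section 2.15.5.2, near the start: "The endpoint will be considered met if the 96% credible interval for the in-hospital event rate is entirely less than the PG".
- Section 2.15.5.2, after Table 3: "The ACP trial will meet its acute safety success if the two-sided 95% credible interval lies entirely below this PG".

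Appendix D then reports under 1.5: "A total of 97 subjects were enrolled in the trial at 17 centers". Under 2.15.3 it replaces each of the three primary tests with a descriptive summary, and under 2.15.6 it drops labeling claims.

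**The concern.** A stated minimum power should agree with the table it summarises, and this one does not. A reader comparing sentence and table cannot tell at once which is wrong. If the table were wrong, the operating characteristics of the whole adaptive design would be in doubt.

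The acute safety claim raises a second question. Power for three primary hypotheses is asserted, but the simulations carry only two. Tables 4a and 4b contain no acute parameter, and section 2.15.5.2 derives the 5% performance goal without assuming a device rate. Two credible-interval levels for one primary test would also leave the success rule open at the margin. In a trial still heading for its confirmatory analysis, these points would need settling before data were seen.

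**Working it through.** **1. The plan's own figures.** Intent-to-treat rows of Table 5:

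| Scenario | Efficacy Power | Safety Win | Power |
|---|---|---|---|
| 5 | 0.93 | 0.93 | 0.91 |
| 6 | 0.89 | 0.89 | 0.88 |
| 7 | 0.93 | 0.92 | 0.92 |
| 8 | 0.90 | 0.90 | 0.90 |
| 9 | 0.93 | 0.92 | 0.92 |
| 10 | 0.88 | 0.90 | 0.87 |

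The 91% for Scenario 5 agrees. The minimum of the Power column is 0.87 over Scenarios 5 to 10 and 0.88 over Scenarios 5 to 9, so at least 89% fails on either reading. Over Scenarios 5 to 9, 0.89 is the minimum of both single-endpoint columns. The documents do not show whether the 89% came from there.

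**2. Size against simulation error.** With 1000 simulated trials per scenario, SE = sqrt(p(1 − p)/1000).
- p = 0.88: SE = sqrt(0.88 × 0.12/1000) = 0.0103. The gap to 0.89 is 0.01/0.0103 = 0.97 SE. The 95% interval is 0.860 to 0.900.
- p = 0.87: SE = sqrt(0.87 × 0.13/1000) = 0.0106. The gap is 0.02/0.0106 = 1.9 SE. The 95% interval is 0.849 to 0.891, so this value is borderline.

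**3. Is the table or the sentence at fault?** The design was re-simulated approximately, with 1000 trials per scenario. Inputs were the Table 4b rates, 25 subjects per month, 5% yearly dropout, the Table 1 boundaries, looks every 50 subjects from 400 to 3000, final analyses at 6, 12, 18 and 24 months, and thresholds of 0.988 and 0.992. Joint power was 0.92–0.93 (Scenario 5), 0.89–0.90 (6), 0.91 (7), 0.92 (8), 0.92 (9) and 0.86–0.88 (10). The ranges come from running with and without dropout in the predictive step. All values lie within about 2 points of Table 5. The table's power figures therefore look sound, and the sentence is the slip. The re-simulation is not relied on for sample size: its mean N was about 1790 for Scenario 6 and 1940 for Scenario 10, against 2350 and 2163 in Table 5.

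**4. Acute safety.** The documents give no device rate, so the rates below are assumptions. Device n = 1880 × 2/3 = 1253, using the Scenario 5 mean N and 2:1 allocation. The largest event count whose exact (Clopper-Pearson) upper limit stays below 5% is shown with P(X ≤ that count).

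| Rule | Events allowed | True rate 2.5% | 3.0% | 3.5% | 4.0% |
|---|---|---|---|---|---|
| Two-sided 95% | 47 | 0.997 | 0.946 | 0.718 | 0.360 |
| Two-sided 96% | 46 | 0.995 | 0.926 | 0.665 | 0.307 |

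A Jeffreys prior gives 47 events under both rules, so 96% against 95% moves the limit by 0 or 1 event in 1253. The one-sided bound in section 2.15.3.4 has no level. At 97.5% it coincides with the two-sided 95% rule, and at 98% with the two-sided 96% rule. If 95% one-sided had been meant, 49 events would be allowed, with power 0.809 at a true rate of 3.5%.

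**5. What the current plan uses.** Enrollment stopped at 97, and 97 < 400, so no sample-size look was reached and the operating characteristics in Table 5 do not describe the trial that took place. Appendix D (2.15.3) keeps only descriptive summaries of the three endpoints, to which neither a power figure nor a success threshold applies.

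**The case for a change.** The best case for a correction is that these sentences still stand in the public protocol. Appendix D has no entry for section 2.15.5, so the 89% and the two interval levels were never amended. Simulation error does not excuse a sentence that purports to report a column, because a printed 0.88 or 0.87 is not at least 0.89. Someone borrowing the design would take away a minimum power 1 to 2 points above the table, and a three-endpoint power claim that was never calculated. Correction would be wording only.

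The mismatch itself stands, and so does the missing support for the acute claim. That claim is unsupported rather than shown to be false: under the two-sided 95% rule, acute power is about 95% or higher if the true rate is 3% or less, and falls quickly above that. Two parts carry less weight. Section 2.15.3 itself says the adaptive design contains efficacy and long-term safety and that acute safety is analysed on whatever sample size results, so a careful reader would not take Table 5 to cover all three. And an interval without a level is under-specified, not a third conflicting rule. What remains is a matter of record that no decision in this trial depends on.

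**Conclusion.** No change to the plan. The 89% is a clerical mismatch with Table 5, whose minimum is 0.87 over Scenarios 5 to 10. The 1–2 point gap is about 1 to 1.9 Monte Carlo standard errors, and the re-simulation supports the table, so it is not evidence of an underpowered design. The acute power claim lacks a calculation, and the 95% and 96% levels differ by at most one allowable event in 1253 device subjects. The acute figures rest on assumed true rates of 2.5% to 4.0%, a device sample fixed at two thirds of the Scenario 5 mean, and the 96% interval being two-sided.

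The deciding point does not depend on those assumptions. Appendix D ended enrollment at 97, made all three primary endpoints descriptive and dropped labeling claims. Rewording the superseded text would alter no sample size, analysis or permissible conclusion. If enrollment and the confirmatory tests were ever reinstated, one interval level and an acute device rate would have to be fixed first.
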